10.3. Potential Benefits to Subjects

There are no potential benefits to patients in this study

10.4. Alternatives to Participation

There are no alternatives to participation available for study subjects given the design of the study

11. CONFIDENTIALITY OF DATA AND INFORMATION STORAGE

It will be the responsibility of the primary investigator (PI) for data collection and storage in a safe, secure area and password protected computer when identifying eligible patients. Research Electronic Data Capture (REDCap) will be used for data collection and storage. Patient confidentiality will be maintained by recording only de-identified data onto the data collection form. Although the data collected and stored in REDCap will be exported for analysis, the exported data will contain no unique, patient-identifying information.

12. RESEARCH INFORMATION IN MEDICAL RECORDS

No research information will be included in the patient's medical record.

13. DATA ANALYSIS AND MONITORING

13.1. Sample Size Determination

There are limited data for proper evaluation of a sample size. However, there was a smaller presented study that had a dramatic decrease in norepinephrine dose in patients on a β -blockers or ACE-inhibitors prior to admission for patients in circulatory shock of any kind.⁷ Using these data, estimated 48h cumulative mean dose for norepinephrine patients not on anti-hypertensives will be 50 mg (SD = 10) and estimated 48h cumulative mean dose for norepinephrine for beta blocker, ACE-Inhibitor, and beta-blocker + ACE-Inhibitor groups will be 25 mg (SD = 10). Using a 4-way fixed effects ANOVA power calculation with estimated effect size from previous study ($f = 1.08$) the total sample size would be 16

F tests – ANOVA: Fixed effects, omnibus, one-way

Analysis: A priori: Compute required sample size

Input: Effect size f	= 1.0825318
α err prob	= 0.05
Power (1- β err prob)	= 0.95
Number of groups	= 4
Output: Noncentrality parameter λ	= 23.4375020
Critical F	= 3.2388715
Numerator df	= 3
Denominator df	= 16
Total sample size	= 20
Actual power	= 0.9609969

However, the current proposed study is specifically looking at septic shock and the anticipated effect is unknown. Therefore, using a 4-way fixed effects ANOVA power calculation with a medium effect ($f = 0.25$) has a total sample size of 180 patients.

F tests – ANOVA: Fixed effects, omnibus, one-way

Analysis: A priori: Compute required sample size

Input: Effect size f	= 0.25
α err prob	= 0.05
Power (1- β err prob)	= 0.80
Number of groups	= 4
Output: Noncentrality parameter λ	= 11.2500000
Critical F	= 2.6559389
Numerator df	= 3

Denominator df	= 176
Total sample size	= 180
Actual power	= 0.8039869

A list of ICU patients will be generated by the corresponding ICD-9 and ICD-10 codes for septic shock during the inclusion time frame, randomized and screened until reaching the minimum power and equal groups (n = 200, 50 patients in each group)

13.2. Planned Statistical Analysis

All data will be reported using descriptive statistics with mean (SD) used to describe normally distributed data and median (interquartile range [IQR]) used for non-normal data or data with a significant number of outliers. Distribution of data and assessment of normality will be analyzed. Chi-squared, Fisher's Exact and Student's t-test as appropriate will be used to assess differences among the study cohorts. A 4-way fixed effects ANOVA will be utilized for the primary outcome, cumulative vasopressor dose at 48 hours. *Post hoc* pairwise comparisons will be completed between groups using Bonferroni's, Turkey, or Hochberg's GT2 depending on final group size and variance. Statistical support for data evaluation will be sought out if necessary.

REFERENCES

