1.2. Purpose of the study

- The primary objective is to determine the effect of chronic β -blocker or ACE-inhibitor on cumulative vasopressor dosing in the first 48 hours of septic shock.
- The secondary objectives of this study
 - To determine the effect of chronic β -blocker or ACE-inhibitor on cumulative vasopressor dosing in the first 6, 12, and 24 hours of septic shock.
 - To determine the effects of chronic β -blocker or ACE-inhibitor on:
 - Adequate fluid resuscitation
 - Cumulative inotrope use (48 hours)
 - Cumulative hydrocortisone use at 6, 12, 24, and 48 hours
 - To determine cumulative vasopressor dose of patients on chronic calcium channel blocker or other antihypertensives (clonidine, hydralazine, angiotensin-receptor-blocker (ARB))

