2. STUDY DESIGN

2.1. Overview

This will be a retrospective four-cohort study. The four cohorts will be septic shock patients that were: 1) not on either a chronic β -blocker or ACE-Inhibitor, 2) on chronic β -blocker, 3) on chronic ACE-Inhibitor, and 4) on both chronic β -blocker and ACE-inhibitor

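### Section 13.2 names only a two-group test for continuous comparisons among four cohorts outside the 48-hour primary outcome, and leaves unclear whether the post hoc correction reaches the secondary outcomes.

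*Combined protocol and SAP*

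**What the plan says.** Section 2.1 sets the design: "This will be a retrospective four-cohort study". The cohorts are neither drug, β-blocker only, ACE-inhibitor only, and both.

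Section 1.2 lists secondary objectives that include "cumulative vasopressor dosing in the first 6, 12, and 24 hours of septic shock". It also lists cumulative hydrocortisone use at 6, 12, 24 and 48 hours, cumulative inotrope use over 48 hours, and adequacy of fluid resuscitation.

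The analysis text in Section 13.2 has three parts that matter here:

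- General comparisons: chi-squared, Fisher's exact and "Student's t-test as appropriate will be used to assess differences among the study cohorts". No outcome is named.
- Primary outcome: "A 4-way fixed effects ANOVA will be utilized for the primary outcome, cumulative vasopressor dose at 48 hours".
- Follow-up comparisons: post hoc "pairwise comparisons will be completed between groups using Bonferroni's, Turkey, or Hochberg's GT2 depending on final group size and variance" (the second method is evidently Tukey's). This comes straight after the ANOVA sentence and does not say which outcomes it covers.

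The same section expects that some data will be non-normal and will be summarised by median and interquartile range, but it names no rank-based test.

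**The concern.** Student's t-test cannot compare four cohorts in one test. Of the three tests in the general sentence, the other two are for categorical data. The phrase about appropriateness therefore leaves only the t-test for a continuous variable. An analyst following the sentence must choose which of the six possible pairs to test and whether to adjust, and the plan settles neither.

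The 6-, 12- and 24-hour doses are the primary measure taken at earlier times. On one reading, the 48-hour result gets an omnibus test and corrected follow-up while the earlier time points get uncorrected two-group tests. Results at the different times would then not be comparable, and false-positive findings on the secondary objectives would be more likely. Because the data already exist, the choice of pairs and of adjustment could also be made after results are seen.

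**Working it through.** **Inputs**

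- Cohorts: k = 4 (Section 2.1), so there are 4 × 3 / 2 = 6 pairs, of which 3 involve the no-drug cohort.
- Group size: Section 13.1 plans 50 per group (200 in total); its calculation gives 180 (45 per group).
- Significance level: Section 13.1 gives "α err prob = 0.05" for the omnibus F test. No level or sidedness is stated for the t-tests, so two-sided 0.05 is assumed.
- Null case: all four cohort means equal, normal data, equal SDs.

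**The plan's own figure.** Section 13.1 uses "Input: Effect size f = 0.25" and "Power (1- β err prob) = 0.80". With N = 180, λ = N·f² = 180 × 0.0625 = 11.25, with 3 and 176 degrees of freedom. The critical F is 2.6559 and the power 0.8040, which match the printed output. N = 176 gives 0.794, so 180 is the smallest balanced total. The plan's figure reproduces, but it concerns the omnibus F test only. The documents state no false-positive rate for the t-tests.

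**All six pairs, unadjusted.** With a common variance estimate, at least one of the six tests is significant when the largest difference between means exceeds the t threshold. That probability is P(q(4, df) > √2 × t(0.975, df)), where q is the studentized range.

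- 50 per group: df = 4 × 49 = 196, t = 1.972, √2 × t = 2.789, probability 0.202.
- 45 per group: df = 4 × 44 = 176, t = 1.974, √2 × t = 2.791, probability 0.202.

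Simulating ordinary two-sample Student t-tests (100,000 data sets) gives 0.202 and 0.203. Treating the six tests as independent would give 1 − 0.95⁶ = 0.265, which is too high because the pairs share cohorts.

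**Only the three pairs against the no-drug cohort, unadjusted.** Simulation at 50 per group gives 0.125. Independence would give 1 − 0.95³ = 0.143, again too high.

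**Corrected, or omnibus first**

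- Bonferroni over six pairs: each test at 0.05 / 6, t(1 − 0.05/12, 196) = 2.665, √2 × t = 3.769, probability 0.041.
- Omnibus F test first, at 50 per group: simulated 0.049.

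**Summary, per continuous outcome with no true difference**

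| What is done | Chance of at least one false positive |
|---|---|
| Six unadjusted t-tests | 20.2% |
| Three unadjusted t-tests against no-drug | 12.5% |
| F test first | 4.9% |
| Six Bonferroni-adjusted t-tests | 4.1% |

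**Sensitivity of the 20%.** Section 3.1 says group sizes will vary, whereas Section 13.1 plans equal groups. With assumed sizes of 110/50/25/15 and equal SDs, six unadjusted tests give 19.6%. With assumed lognormal data at 50 per group they give 17.9%.

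**The case against.** The strongest reply is that the text prescribes none of what produces 20%. The general sentence names no outcome, does not call for all six pairs, and does not say the tests are unadjusted. It follows the descriptive-statistics sentences and may be meant for baseline characteristics. The correction sentence is not expressly limited to the primary outcome. If it covers all pairwise comparisons, the rate is about 4%. Testing each drug cohort only against no-drug, which fits the hypothesis in Section 1.1, gives about 12.5%.

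Most of this stands. A reader might infer that the secondary outcomes carry a 20% false-positive rate under the plan as written. The documents do not support that; 20% is the top of a range. A reader might also infer that unequal cohorts push the rate well beyond 20%. Unequal sizes alone do not. Unequal variances could, but the documents give no SDs for the secondary outcomes, and an ordinary F test would be affected too.

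The reach is also limited. Section 1.2 does not say whether hydrocortisone use, inotrope use and fluid adequacy are amounts or yes/no. If they are yes/no, chi-squared and Fisher's exact already handle four groups. The 48-hour primary analysis is not affected.

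The reply does not remove the gap. If the general sentence is for baseline data only, the secondary outcomes have no stated test at all. On the generous reading of the correction sentence, there is still no omnibus test for them.

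**Conclusion.** The point holds as a gap in specification. Outside the 48-hour primary outcome, the only test named for continuous data is a two-group test in a four-cohort study, and the scope of the multiplicity correction is unclear. The outcomes clearly affected are vasopressor dose at 6, 12 and 24 hours; hydrocortisone and inotrope use join them if analysed as doses.

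Depending on how the section is read, the false-positive rate per outcome runs from about 4 to 5%, through about 12.5%, up to about 20%. These figures assume no true difference, two-sided 0.05 per test, normal data, equal SDs and about 50 per cohort. They are per outcome and do not address multiplicity across outcomes. Since only secondary outcomes of a retrospective review are touched, this should be corrected before analysis but does not threaten the primary result.

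**What to change.** In Section 13.2, replace Student's t-test with one-way ANOVA across the four cohorts for continuous variables, using Welch ANOVA if variances are unequal and Kruskal-Wallis if the data are non-normal. Add that the corrected post hoc comparisons used at 48 hours also apply to vasopressor dose at 6, 12 and 24 hours and to the other continuous secondary outcomes. State which of the hydrocortisone, inotrope and fluid outcomes are analysed as amounts and which as yes/no, so that the test for each is clear.

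The cost is a sentence or two, with no new data and no change to the sample size. The downside is that some secondary p-values will be less favourable than unadjusted t-tests would give.

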1.3. Background

Literature suggests that extended periods of tachycardia, in patients with shock, are associated with increased mortality.¹⁻⁴ Interventional trials have suggested that increased doses of catecholamines are associated with the increased mortality and the administration of esmolol infusions may improve survival in patients with shock requiring vasopressor agents.¹

What remains unknown is the effect of home exposure to antihypertensive therapies, specifically beta-blockers and ACE-inhibitor. This study will evaluate the effects of home antihypertensive therapy with beta-blockers and ACE-inhibitor on vasopressor dose administered within the first 48 hours of septic shock.

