3. CHARACTERISTICS OF THE RESEARCH POPULATION

3.1. Subject Characteristics

Number of Subjects:

It is estimated that approximately 200 patients will be included for this study. The individual number for each group will vary based on screening.

Gender and Age of Subjects:

No restrictions apply to gender of the study subjects. Only adult, non-pregnant patients will be included, defined as 18 years of age or older.

a) Racial and Ethnic Origin:

No restrictions apply to race or ethnic origin of the study subjects.

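### The objective is the effect of home β-blocker or ACE-inhibitor use, but the only primary analysis is a one-way ANOVA on cohort that uses none of the confounders the study collects

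*Combined protocol and SAP*

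**What the plan says.** - **Aim.** Section 1.2 makes the effect of chronic β-blocker or ACE-inhibitor use on 48-hour cumulative vasopressor dose the primary objective. Section 1.3 repeats it: "This study will evaluate the effects of home antihypertensive therapy with beta-blockers and ACE-inhibitor on vasopressor dose". The hypothesis in 1.1 is worded only as an association.
- **Design.** Sections 2.1 and 4.1 define four retrospective cohorts by home medication: neither drug, β-blocker, ACE-inhibitor, both. Section 2.2 says many of these patients have comorbidities that require the drugs.
- **Primary analysis.** Section 13.2: "A 4-way fixed effects ANOVA will be utilized for the primary outcome, cumulative vasopressor dose at 48 hours". Post hoc pairwise comparisons follow. The power output in 13.1 is headed "ANOVA: Fixed effects, omnibus, one-way", with four groups.
- **Baseline differences.** Section 13.2 has chi-squared, Fisher's exact and t-tests that "as appropriate will be used to assess differences among the study cohorts". No section names a covariate, a match, a weight or a propensity score.
- **Data.** Section 5.1 collects age, gender, weight, a list of comorbidities, the Charlson index and other home antihypertensives.

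**The concern.** Patients who take a β-blocker or an ACE-inhibitor at home are likely to differ from those who take neither in age, cardiac and renal disease and other home drugs. Any of these may also be related to vasopressor dose. The planned test compares raw cohort means, so it measures the drug difference and the patient difference together. The bias could create an apparent dose-sparing effect or hide a real one. Screening more charts would not help: it estimates the same mixed difference more precisely.

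Co-medication is a concrete example. For the first scenario in 13.1, the "cumulative mean dose for norepinephrine patients not on anti-hypertensives will be 50 mg". Cohort 1 as defined in 2.1 and 4.1 lacks only a β-blocker and an ACE-inhibitor. It may include users of ARBs, calcium channel blockers, clonidine or hydralazine, and so may the other three cohorts. Section 1.2 lists these drugs as of interest for vasopressor dose, yet the primary comparison ignores them.

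**Working it through.** **1. What the ANOVA is.** Section 13.2 calls it 4-way, but no four factors are named anywhere. The 13.1 output has numerator df 3 = 4 − 1 and denominator df 176 = 180 − 4. Cohort is the only term, and no degrees of freedom are set aside for covariates.

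**2. The plan's own figure.** Inputs from 13.1: f = 0.25, α = 0.05, four groups, N = 180. Noncentrality λ = N·f² = 180 × 0.0625 = 11.25; critical F(3, 176) = 2.6559; power = 0.804. This matches the document. At the planned 200 charts, λ = 12.5 and power is 0.848. Both figures are for the unadjusted test.

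**3. False positives if cohort 1 is shifted by confounding.** The documents give no imbalance or correlation, so the shift s (in SDs of dose) is assumed. With no drug effect, n₁ patients in cohort 1 and N = 200:

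λ = n₁(N − n₁)/N × s². For n₁ = 50 this is 37.5·s², tested on df 3 and 196.

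| s (assumed) | λ | Rejects with no drug effect |
|---|---|---|
| 0 | 0 | 5% |
| 0.09 | 0.30 | 6.8% |
| 0.20 | 1.50 | 15.1% |
| 0.40 | 6.00 | 50.9% |

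A shift of 0.20 SD arises, for example, if one confounder differs by 0.5 SD between cohort 1 and the rest and correlates 0.4 with dose (0.5 × 0.4 = 0.20). In 2,000 simulated studies of that case the unadjusted test rejected in 15.4%, and the test adjusted for that confounder in 4.8%.

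**4. Masking.** Suppose f = 0.25 arises from cohort 1 differing equally from the other three (assumed pattern). The contrast is then 0.25/(√3/4) = 0.577 SD. If a 0.20 SD bias opposes it, 0.377 SD remains, λ = 37.5 × 0.377² ≈ 5.34, and power falls from 0.85 to 0.46.

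**5. What adjustment does to power.** λ = N·f²·(1 − R²x)/(1 − R²y). R²y is the share of within-cohort dose variance that the covariates explain; R²x is the share of the cohort contrast that they explain. Both are assumed. At N = 200 with 10 covariates (df 3 and 186):

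| R²y | R²x | λ | Power |
|---|---|---|---|
| 0 | 0 | 12.50 | 0.85 |
| 0 | 0.3 | 8.75 | 0.69 |
| 0.3 | 0.3 | 12.50 | 0.85 |
| 0.3 | 0 | 17.86 | 0.95 |

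Power can go either way. Using 20 covariates instead of 10 changes it by about 0.001, so what matters is how strongly the covariates predict cohort, not how many there are.

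**The case against.** **The hypothesis claims only association, and the design is exploratory.** This is the strongest reply, and part of it stands. An unadjusted test can address 1.1, and 2.2 gives limited knowledge as the reason for a retrospective study. But 1.2 and 1.3 ask about effect, and the plan has a named primary outcome and a formal power calculation. The answer to the stated objective is what readers will look for.

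**Other parts of the plan might already deal with it.** They do not. In 13.1 the chart list is "randomized and screened until reaching the minimum power and equal groups", which randomises the order of screening, not exposure. Stratifying into four groups in 4.1 defines exposure. The baseline tests can show imbalance but cannot correct it. Seeking statistical support if needed is not a prespecified model.

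**Adjustment costs power and does not prove causation.** Both are fair. Power may fall, and unmeasured confounding remains, so an adjusted model also supports only an association, though one with less bias.

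**The 50 mg figure belongs to a scenario that 13.1 sets aside.** Correct. The total of 180 rests on f = 0.25, so the mismatch with cohort 1 illustrates co-medication and is not an error in the adopted sample size.

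**Conclusion.** The point holds as a should-fix. The plan asks for an effect, says why exposure is tied to comorbidity, collects the relevant variables, and then analyses cohort alone. That conclusion rests on the text and not on any assumed figure.

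The size and direction of the bias are unknown. A reader might infer from the table that this study has a 15% or 51% false-positive rate. The documents do not support that: every shift is assumed, and the calculation takes 50 per group from 13.1, whereas 3.1 says "The individual number for each group will vary based on screening". At N = 200 with 20 or 80 patients in cohort 1, the 0.20 SD shift gives 9.5% or 18.3%.

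A reader might also infer that the sample size is wrong or must rise. It need not: 180 is correct for the unadjusted test, and adjusted power may be higher or lower. Nor does the omission make the study unusable, since the covariates are already being collected and the model can be added before analysis.

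**What to change.** **In 13.2:**
- Make the primary analysis a linear model of 48-hour cumulative dose on cohort (four levels, joint 3-df test) plus a short set of pre-shock covariates from 5.1, fixed before doses are analysed. An example set is age, sex, weight, Charlson index, hypertension, heart failure, CKD, CAD, atrial fibrillation/flutter and use of other home antihypertensives, with the drugs counted under that term listed.
- Report adjusted differences of cohorts 2, 3 and 4 from cohort 1 with 95% confidence intervals. Keep the unadjusted ANOVA as supportive.
- Leave peak lactate, fluids, hydrocortisone and SOFA out of the primary model. They may follow from exposure, and 5.1 does not say when SOFA is scored.
- Tabulate covariates by cohort and report poor overlap as a limitation. Do not drop a covariate because it is imbalanced, since that removes the strongest confounders. If hypertension prevalence in the three treated cohorts were 85%, 90% or 95% (assumed), a rule dropping covariates with fewer than 5 patients at either level in any cohort would discard it with probability of at least 30%, 82% or over 99% (binomial, 50 per cohort).
- Word conclusions as adjusted association.

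**In 13.1:** state that 0.80 power at N = 180 (0.85 at N = 200) is for the unadjusted test and that adjusted power may be higher or lower. No numeric range needs to be written in, because the inputs are unknown.

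**Cost:** SAP wording, one regression and one table, using variables already on the collection list. Power may fall if the covariates strongly predict cohort. Rewording 1.2 and 1.3 as unadjusted association is the minimum alternative, but it gives up the question the study set out to answer.

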1. PURPOSE OF THE STUDY AND BACKGROUND

1.1. Hypothesis

- Chronic β -blocker or Angiotensin-Converting Enzyme (ACE)-inhibitor use is associated with decreased cumulative doses of vasopressors administered in the first 48 hours of septic shock

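### The primary hypothesis compares users with non-users, but no such comparison is given priority and power is stated only for the four-group omnibus F test

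*Combined protocol and SAP*

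**What the plan says.** Section 1.1 states a directional hypothesis: chronic β-blocker or ACE-inhibitor "use is associated with decreased cumulative doses of vasopressors administered in the first 48 hours of septic shock". Section 1.2 repeats it as the objective ("The primary objective is to determine the effect of chronic" β-blocker or ACE-inhibitor on that dose). Section 2.1 sets the design: "This will be a retrospective four-cohort study". Cohort 1 takes neither drug, cohort 2 a β-blocker, cohort 3 an ACE-inhibitor and cohort 4 both.

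Section 13.2 assigns the test: "A 4-way fixed effects ANOVA will be utilized for the primary outcome, cumulative vasopressor dose at 48 hours". The power output in 13.1 labels this a one-way omnibus test, and it is read that way here. Then "pairwise comparisons will be completed between groups using Bonferroni's, Turkey, or Hochberg's GT2 depending on final group size and variance". After a four-group ANOVA the ordinary reading is all six pairs.

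Section 13.1 contains two calculations. The first takes a non-user mean of 50 mg (SD 10), while the "beta blocker, ACE-Inhibitor, and beta-blocker + ACE-Inhibitor groups will be 25 mg (SD = 10"). The second is the operative one. It concedes that "the current proposed study is specifically looking at septic shock and the anticipated effect is unknown", takes f = 0.25, and "has a total sample size of 180 patients"; the target is then set at 200, with 50 per group. No power is given for any pair or contrast. Section 3.1 says instead that group sizes will vary with screening.

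**The concern.** The F test has three numerator degrees of freedom and no direction. It can be significant because user cohorts differ from one another, or because users need more vasopressor. The hypothesis is therefore settled by the follow-up tests, and the plan neither ranks nor powers them.

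The wording of 1.1 and 1.2 allows at least three targets: each user cohort against cohort 1, any use against none, or each drug's main effect in the 2×2 that the cohorts form. Section 13.2 chooses none of them. If some user cohorts differ significantly from cohort 1 and others do not, the plan does not say what follows. Such a split could be misread as a difference between drug classes.

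**Working it through.** **1. The plan's own figure.** With λ = N f² and critical value F(0.95; 3, N − 4):
- N = 180: λ = 180 × 0.0625 = 11.25, critical F = 2.6559, power = 0.804. This matches 13.1.
- N = 200: λ = 12.5, power = 0.848.

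**2. Assumed mean pattern.** Section 13.1 gives no means for f = 0.25, so its first pattern is borrowed: cohort 1 differs and the three user cohorts are equal. For a difference of d SDs,

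f² = ¼[(3d/4)² + 3(d/4)²] = (3/16)d².

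Check: d = 25/10 = 2.5 gives f = 2.5 × √(3/16) = 1.0825, as printed in 13.1. Rescaled to f = 0.25, d = 0.25/√(3/16) = 0.577. The 50 mg group in 13.1 takes no antihypertensives at all, whereas cohort 1 only lacks the two study classes, so this is an approximation.

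**3. Power for one user-versus-none pair.** The noncentrality is d√(n/2): 0.577 × √22.5 = 2.74 at n = 45, and 0.577 × 5 = 2.89 at n = 50. Pooled error df are 176 and 196. The Welch–Holm row is simulated, two-sided at 0.05.

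| Method | Critical value, n = 45/50 | Power, n = 45/50 |
|---|---|---|
| Bonferroni, six pairs | 2.668/2.665 | 53%/59% |
| Hochberg GT2, six pairs | 2.660/2.657 | 53%/59% |
| Tukey | 2.594/2.591 | 56%/62% |
| Bonferroni, three pairs | 2.417/2.415 | 63%/68% |
| Welch–Holm, three pairs | – | 70%/75% |

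**4. The three comparisons with cohort 1 taken together (simulation, n = 45/50).**

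| | Tukey | Welch–Holm |
|---|---|---|
| At least one significant | 79.8%/84.3% | 84.6%/88.3% |
| All three significant | 30.9%/37.1% | 54.8%/61.4% |
| Mixed (difference of the two rows) | 49%/47% | 30%/27% |

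Relative reduction in mixed results: 1 − 30/49 = 39% and 1 − 27/47 = 43%, so about 40%.

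**5. Other patterns with f = 0.25.** Tukey power for one truly differing pair:
- the two extreme cohorts (d = 0.71): 78%/83%
- a two-two split (d = 0.50): 41%/47%
- a cohort midway between the extremes (d = 0.35): 18%/21%

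Welch–Holm was higher than Tukey for every truly differing user-versus-none pair in the patterns checked.

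**6. Any use versus none as one contrast of cohorts 2–4 against cohort 1.** Power is 92%/94% under the pattern in step 2, 49%/53% in a two-two split, and 20%/22% if only one user cohort differs.

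**7. Unequal variances.** As ANOVA follow-ups, all three named procedures use the pooled variance. With no true differences, 50 per group and SDs in the ratio 2:1:1:1 (assumed, cohort 1 the most variable), the chance of a false claim in the three comparisons with cohort 1 is 6.4% to 6.5% with Tukey across simulation runs, against 3.5% to 3.6% with Welch–Holm. With equal SDs and no true differences, Welch–Holm gives 4.5%/4.4%.

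**The case against.** An omnibus test followed by adjusted pairwise tests is standard practice. Read as all six pairs, 13.2 does perform the three user-versus-none tests and does adjust them. That stands: a reader might infer that multiplicity is ignored, and the text does not support this. What is missing is priority among the pairs and the power of those that matter.

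A reader might also infer that leaving the adjustment open until group sizes and variances are seen inflates error. With equal groups and equal variances it does little harm. Tukey has the smallest critical value of the three, so the most favourable choice is simply Tukey, which controls the familywise error; the three differ by about 3 points of power. The real limit is that none of them handles unequal variances, so choosing among them by variance does not help.

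The hypothesis says *or*, and a mixed result is a problem only if all three comparisons matter. On an at-least-one reading the plan reaches 80%/84%, close to its stated omnibus power. This also stands, and it limits the point. But the plan does not adopt that reading.

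Finally, the figures depend on an assumed pattern and on equal groups, which 3.1 does not promise. The missing designation depends on neither.

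**Conclusion.** The point holds as a mismatch between the hypothesis and the test that is powered. A reader might infer that the sample size is miscalculated or that the study is bound to fail. Neither follows: 180 is correct for the omnibus test, and the study would usually find at least one difference if the assumed pattern is true.

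Under that pattern, with equal groups of 45/50, naming the three comparisons with cohort 1 and using Welch–Holm raises power per comparison from 56%/62% (Tukey) to 70%/75%. It cuts mixed results by about 40% but does not remove them. On the at-least-one reading the gain is small: 80%/84% becomes 85%/88%. The study remains analysable as written, so this is a change that should be made rather than a fatal flaw.

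**What to change.** In 13.2, name cohorts 2, 3 and 4, each against cohort 1, as the confirmatory comparisons, using Welch tests with Holm adjustment over the three. State that the ANOVA is supportive, so that there is one route to success; if either F or Welch–Holm could claim success, the null error would be 6.5% to 6.6%. If F is kept as a gate, say so and quote 68%/74% per comparison. Make comparisons among cohorts 2–4 secondary, with one named method.

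If the sponsor means any use versus none, or each drug's main effect in the 2×2, name that contrast in place of the three comparisons, with a variance-robust test and its own power. A single planned contrast or a fixed Tukey procedure would also settle which test decides, though Tukey would leave the pooled-variance problem.

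In 13.1, say that 80%/85% applies only to the equal-size omnibus test. Add the power of the chosen comparison with its mean-pattern and equal-group assumptions (Welch–Holm about 70%/75% per comparison). State that significance in one user cohort and not in another is not evidence of a drug-class difference. Reconcile 3.1 (group sizes vary) with 13.1 (50 in each group).

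Cost: wording in 3.1, 13.1 and 13.2, and no extra patients. The ANOVA loses its confirmatory role, comparisons among user cohorts become secondary, and the stated power per comparison is below 80%.
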